## 6.2 Power Simulations for Primary Objective 2 Outcome

### 6.2.1 Description of Power Simulation

We investigated the power of the primary Objective 2 analysis via Monte Carlo simulation. We assumed the following sample sizes for the number of patients with a prior OUD diagnosis over a 3-year period from the Phase 1 data, reflecting the 3-year baseline period of PROUD during which patients with an OUD diagnosis will be identified:

site_id	clin_num	Clin	nOUD
A	1	A1	9
A	2	A2	12
C	1	C1	63
C	2	C2	39
E	1	E1	58
E	2	E2	200
I	1	I1	100
I	2	I2	49
J	1	J1	27
J	2	J2	10
K	1	K1	388
K	2	K2	290

We generated individual-level outcome data within each of the 12 clinics as follows. First, we randomly assigned one of the two clinics within a HCS to receive the PROUD intervention and the other to the Usual Primary Care (UPC) group. We then generated outcome data from a Poisson distribution with mean number of acute care days over a two-year period (time-frame of PROUD outcome ascertainment) using the following mean model,

$$\log E(y_{ijk}) = \alpha + \beta * trt_{ij} + \theta_{ij}$$

where

- 1)  $y_{ijk}$  is the number of days of acute care utilization of patient  $k$  in clinic  $i$  of HCS  $j$
- 2)  $trt_{ij}$  is the treatment indicator (PROUD intervention versus UPC) for clinic  $i$  in HCS  $j$
- 3)  $\theta_{ij} \sim N(0, \tau^2)$  is the random effect for clinic  $i$  in HCS  $j$  ( $\tau$  is the standard deviation of the clinic-level random effect)

For the parameter  $\alpha$  we assumed that the baseline rate of acute care utilization over a two-year period for patients assigned to a UPC clinic was equal to the average number of acute care visits among patients with a prior OUD diagnosis obtained from Phase 1 data (=4.0 visits) multiplied by the average number of days per acute care visit. The average number of days per acute care visit was based on data from one health system on the average length of stay among all patients (since length of stay data was not available from all health systems at Phase 1), which was 2.04 days per visit. That is, we assumed  $\alpha = \log(4 * 2.04) = 2.1$ . We considered a range of values for the intent-to-treat relative risk parameter  $RR_{ITT} = \exp(\beta)$  governing the association between being assigned to the PROUD intervention and acute care utilization over the follow-up period. Finally, we considered three different values for the standard deviation  $\tau$  of the clinic-level random effect  $\theta_{ij}$ . Specifically, we estimated a value for  $\tau$  using Phase 1 data of  $\tau = 0.23$ , and also considered two values as a sensitivity analysis: one that was 50% smaller ( $\tau = 0.12$ ) as well as one that was 50% larger ( $\tau = 0.35$ ). We estimated power and type 1 error based on the standard Wald test, as well as the Wald F test that used a denominator degree of freedom based on the Between-Within (BW) small sample degree of freedom correction. For testing the coefficient  $\beta$  from the above model, the BW method uses as denominator degree of freedom ( $10 = 12$  clinics - 2 fixed effect parameters being estimated). Results are based off of 1,000 simulation repetitions.

In addition to presenting power across values of  $RR_{ITT}$ , we also provide additional context in light of the fact that not all individuals in the intervention clinic with an EHR documented OUD diagnosis pre-randomization will visit the PROUD NCM and receive sustained treatment with buprenorphine or injectable naltrexone (hereafter “treated for OUDs”), which is hypothesized to meaningfully reduce acute care utilization. Specifically, for different values of  $RR_{ITT}$ , we report the proportion of patients who would need to be treated for OUDs (denoted by  $p_{treat}$ ), if the relative risk of acute care utilization comparing patients who are treated for OUDs versus patients who are not treated for OUDs ( $RR_{treated}$ ) is 0.1 or 0.2. A value of 0.2 corresponds approximately to the observed RR of acute care visits comparing those without OUD to those with OUD; a value of 0.1 corresponds to the assumption that those who are treated for OUDs will have a 50% decrease in the average visit length compared to those with OUD who are not treated. These calculations assume that patients with OUD in a PROUD intervention clinic who are not treated for OUDs have the same rate of acute care utilization as patients with OUD in UPC clinics.

### 6.2.2 Results of Power Simulations

The following table shows the type 1 error rates for each of the 3 values of clinic-level random effect SD ( $\tau$ ) using the naïve Wald test (“Wald” below), as well as the Wald F test based on the BW degree of freedom correction (BW below):

	$\tau$	Wald	BW
Sensitivity	0.12	0.106	0.075
Primary	0.23	0.104	0.070

[figure not shown]

	$\tau$	Wald	BW
Sensitivity	0.35	0.111	0.067

Although the type 1 error rates using the BW method (0.067-0.075) are still slightly elevated over the nominal 0.05 level, they are much closer to the correct level as compared to the standard Wald test (all > 0.1). We will continue to explore whether this can be improved further as the SAP continues to be developed.

The power (or type 1 error rates for  $RR_{ITT} = 1$ ) across different effect sizes (parameterized by  $RR_{ITT}$ ) and different values of the random-effect SD  $\tau$  (0.12, 0.23, and 0.35) is given in Figure 2:

**Figure 2: Objective 2 Power Across Different Effect Sizes**

Here 'Prej' denotes the proportion of Monte Carlo iterations for which the null hypothesis was rejected; each panel corresponds to a different value of the random-effect SD ( $\tau$ ). Based on using the BW degree of freedom correction approach, we estimated that we have >80% power to detect values of  $RR_{ITT} < 0.65$  when  $\tau = 0.23$ , corresponding to a 35% reduction in the acute care utilization rate among patients in a PROUD versus UPC clinic. Similarly, we have >80% power to detect values of  $RR_{ITT} < 0.80$  when  $\tau = 0.12$  and of  $RR_{ITT} < 0.55$  when  $\tau = 0.35$ .

We next provide additional context on the corresponding proportion of patients in PROUD intervention clinics who would need to be treated for OUDs ( $p_{treat}$ ) in order to detect the above values of  $RR_{ITT}$  when the underlying relative risk of acute care utilization comparing patients treated for OUDs versus those who are not treated ( $RR_{treated}$ ) is 0.1 or 0.2.

	$\tau$	$RR_{ITT}$	Proportion of patients needing to be treated for OUD ( $p_{treat}$ )	
			RR among treated ( $RR_{treated}$ )=	
			0.1	0.2
Sensitivity	0.12	< 0.80	>22%	>25%
Primary	0.23	< 0.65	>39%	>44%
Sensitivity	0.35	< 0.55	>50%	>56%

Thus, under our primary assumption for the random-effect SD ( $\tau$ ) if at least 39-44% of patients with OUD in the PROUD intervention arm at baseline are treated for OUD by the NCM, then we will have over 80% power to detect at least a 35% decrease in acute care utilization ( $RR_{ITT} < 0.65$ )

comparing patients with OUD in the PROUD intervention arm versus UPC, when the true RR comparing treated to untreated patients with OUD ( $RR_{treated}$ ) is 0.1-0.2. If fewer patients are treated, then our power would be less than 80% under these same assumptions.

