7.1.1 PROUD Intervention: Implementation of the MA Model

Overview and Duration. Clinics randomized to the PROUD intervention will be asked to implement collaborative care for OUDs consistent with the MA Model. The intervention is funded for 2 years. This includes 6 months start-up (hiring, training and policy development) and 18 months for induction of an estimated 1-3 patients a week (~75-225 total), as well as continued care with buprenorphine and naltrexone. The intervention consists of 3 strategies used for implementation. These 3 strategies are described immediately below. The detailed outline of each element of the MA Model that will be implemented by PROUD Intervention clinics and the Draft PROUD Manual are described below (Appendix B).

Strategy #1: Providing Funding and Guidance to Hire a NCM. First, Site PIs and health system leaders will be notified they were selected for the trial. A phone meeting will orient them towards hiring even before the in-person kickoff meeting. After kickoff, when clinics randomized to the PROUD intervention will be announced, clinic leaders and providers who have agreed to prescribe buprenorphine and naltrexone will be notified that they will receive resources and support to implement the MA Model. The clinic randomized to the PROUD intervention will be provided funding for 1.0 FTE salary for a NCM for 2 years. The clinic and health system will then recruit, hire, and onboard the NCM, supported by the project. Hiring two NCMs to share a full-time position is also an option.

The nurse care manager (NCM) is a dedicated person in the primary care clinic who works with a group of primary care doctors, nurse practitioners, and physician assistants to support management of patients on buprenorphine and injectable naltrexone for OUDs. Table 5 outlines the roles and responsibilities of the NCM (also included as part of Appendix A).

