10.3.3 Timing of Outcomes Measurement

Initially, we planned to start measurement 6 months after randomization to allow sites up to 6 months to hire the NCM before outcome measurement began. However, several stakeholders pointed out that leaders of health systems would be interested in information on outcomes beginning at the time a decision was made to hire an OBAT NCM, which occurs at randomization in this trial. As a result, based on discussions with the protocol development team, a decision was made to measure outcomes starting at randomization. Process measures will include timing of NCMs and prescribers starting to care for patients with OUDs.

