Because one of the HCSs was randomized at a later date than the others, not all HCSs have the same amount of follow-up time. To account for this difference, we will include in the model an offset term for the number of days of potential follow-up time (e.g., 2 years for 5 of the HCSs and 1.5 years for the 6th HCS); in the above model,  $\log(\text{days}_j)$  denotes the offset term where  $\text{days}_j$  denotes the days of follow up in HCS  $j$ .

We will evaluate our primary Objective 2 hypothesis by testing the null hypothesis  $H_0: \beta = 0$  versus the two-sided alternative hypothesis that  $\beta$  is non-zero with a type 1 error rate of 0.05. In cluster-randomized trials with a small number of clusters, a small-sample correction is often necessary to obtain correct type 1 error rates. Although small-sample degree of freedom (DF) correction methods have been evaluated for continuous and binary outcomes under generalized linear mixed-effect models (GLMMs), there has not been prior guidance of which approach to use in our setting with a count outcome and covariate adjustment. Given this lack of knowledge, members of the PROUD statistical team are conducting simulations to evaluate alternate small-sample DF methods in this setting. Our results so far suggest that the optimal choice of testing procedure varies depending on the data-generating scenario in terms of the intraclass correlation

coefficient (ICC), number of clusters, and sample size within a cluster; however, using the likelihood ratio test with the Between-Within (BW) DF correction method (also referred to as “inner-outer” approach) appears to perform generally well in the scenario that aligned most closely with PROUD Phase 1 data used in the power simulation (see Appendix C).

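### The SAP's 39-44% treated threshold for over 80% Objective 2 power assumes, without saying so, that treatment acts from the day of randomization

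*SAP*

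**What the plan says.** SAP 6.2.1 models acute care days over two years and finds the RR_ITT detectable at each clinic-level random-effect SD (tau). It then translates RR_ITT into coverage: "we report the proportion of patients who would need to be treated for OUDs", for RR_treated of 0.1 or 0.2. On the source of the larger value it says: "A value of 0.2 corresponds approximately to the observed RR of acute care visits comparing those without OUD to those with OUD". The value 0.1 adds a halving of visit length. The only rate assumption stated for this step is that intervention-clinic patients "who are not treated for OUDs have the same rate of acute care utilization as patients with OUD in UPC clinics". Nothing is said about when treatment begins.

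SAP 6.2.2 sets a coverage condition at tau = 0.23: "if at least 39-44% of patients with OUD in the PROUD intervention arm at baseline are treated for OUD by the NCM". Where that condition is met, the SAP draws this conclusion about power: "then we will have over 80% power to detect at least a 35% decrease in acute care utilization". The Objective 2 test is two-sided: the alternative is that the treatment coefficient "is non-zero with a type 1 error rate of 0.05" (SAP 5.3).

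On timing, protocol 10.3.3 records that "a decision was made to measure outcomes starting at randomization". Protocol 7.1.1 says of the two funded years: "This includes 6 months start-up (hiring, training and policy development) and 18 months for induction of an estimated 1-3 patients a week". Protocol Table 3 describes months 7 to 24 as a ramp-up. Protocol 9.3.2 and 9.3.3 allow one to six months for hiring and place NCM training about four months after randomization. SAP 5.2.2 accepts that hiring and first patients took time. SAP 5.3 nevertheless analyses the full follow-up by intention to treat.

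**The concern.** A patient who will eventually be treated by the NCM accrues acute care at the untreated rate until treatment starts, and those days count in the outcome. A coverage threshold that ignores this waiting time is too low. At stake is how an Objective 2 result is read. A trial that reached 39-44% coverage could be described as having met the SAP's condition for over 80% power when, on its own schedule, it had not.

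**Working it through.** **Inputs.** From SAP 6.2.1-6.2.2: target RR_ITT 0.65 at tau 0.23; RR_treated 0.1 or 0.2; control mean 4.0 x 2.04 = 8.16 days; twelve clinics with the listed numbers of OUD patients; 10 denominator df for the Between-Within (BW) test. Assumed here, because the documents do not give it: the distribution of treatment start times.

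**Reproducing the SAP table.** If untreated patients have the UPC rate, RR_ITT = 1 - p(1 - RR_treated), so p = (1 - RR_ITT)/(1 - RR_treated).

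- tau 0.12: 0.20/0.9 = 22%; 0.20/0.8 = 25%
- tau 0.23: 0.35/0.9 = 39%; 0.35/0.8 = 44%
- tau 0.35: 0.45/0.9 = 50%; 0.45/0.8 = 56%

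All six cells match, so the table gives treated patients RR_treated over the whole window.

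**Reproducing the power.** The simulation drew Poisson counts with a clinic random intercept, used the SAP's clinic sizes, and fitted a random-effects model to clinic log-rates (a normal approximation to the Poisson mixed model), with 20,000 repetitions per cell. At tau 0.23 the type 1 error is 0.105 (Wald) and 0.071 (BW), against the SAP's 0.104 and 0.070. BW power at RR_ITT 0.65 is 85%, consistent with the stated figure of over 80%.

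**Adding the delay.** Let f be the mean share of follow-up after NCM treatment starts, with acute care accruing evenly and no later discontinuation. A treated patient's two-year RR is 1 - f(1 - RR_treated). Hence RR_ITT = 1 - p f (1 - RR_treated), and p = (1 - RR_ITT)/[f(1 - RR_treated)]. At the SAP's coverage, p(1 - RR_treated) = 0.35, so RR_ITT = 1 - 0.35f.

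| Assumed start | f | p needed, RR_treated 0.1 / 0.2 | RR_ITT at 39-44% treated | BW power at 39-44% treated |
|---|---|---|---|---|
| Day 1 (SAP) | 1 | 39% / 44% | 0.65 | 85% |
| All at month 4 | 20/24 = 0.833 | 47% / 53% | 0.71 | 68-69% |
| All at month 6 | 18/24 = 0.75 | 52% / 58% | 0.74 | 58-59% |
| Uniform, months 6-12 | 15/24 = 0.625 | 62% / 70% | 0.78 | 43% |
| Uniform, months 6-24 | 9/24 = 0.375 | 104% / 117% | 0.87 | 19-20% |

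Power ranges reflect a difference of about one point between simulation runs. In the last row even full coverage gives RR_ITT of only 1 - 0.375 x 0.9 = 0.66 or 1 - 0.375 x 0.8 = 0.70.

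The other rows of the SAP table move the same way. With all starts at month 6, p is 30-33% at tau 0.12 (0.20/0.675 and 0.20/0.6) and 67-75% at tau 0.35 (0.45/0.675 and 0.45/0.6). In the health system with 18 months of follow-up, a month-6 start gives f = 12/18, and p at tau 0.23 is 58-66%.

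**The case against.** The strongest defence is that RR_treated is defined as a comparison of treated with untreated patients, within a model of two-year counts. Read as a two-year average, the formula is exact, and the conclusion is explicitly conditional on that RR. This shows that the divisions are correct; a reader might infer an arithmetic slip, and there is none. It does not rescue the values chosen. With a month-6 start, zero acute care afterwards still leaves a two-year RR of 1 - 0.75 = 0.25. With a month-4 start the floor is 1 - 0.833 = 0.17, so 0.1 is impossible, and 0.2 requires an on-treatment RR of (0.2 - 0.167)/0.833 = 0.04. The SAP also anchors 0.2 on a contrast between people with and without OUD, which contains no waiting period.

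Three further points stand. First, month 6 is not the most favourable case, because protocol 9.3.2-9.3.3 allow earlier starts; hence the month-4 row. Second, a reader might infer from protocol 7.1.1 that starts are uniform over months 6-24 and that the target is therefore unattainable. That section gives a programme-wide induction pace. It does not say starts are uniform, and it does not describe the Objective 2 sample, who already had an OUD diagnosis and a clinic visit before randomization. SAP 5.5.1 expects many treated patients to be new to the clinic. Third, the SAP offers the table as context and warns that power falls if fewer are treated. It also prespecifies Objective 2 analyses restricted to the period when the NCM was seeing patients (5.4.5), which limits the scope for misreading a null result.

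**Conclusion.** The concern holds as an undisclosed full-exposure assumption that conflicts with the documented schedule. The direction is certain for any delay in starting treatment. The size depends on f, which is assumed: from 47-53% (everyone at month 4) to above 100% (uniform over months 6-24), with power at 39-44% treated falling to between about 69% and 19%. Discontinuation after starting is not modelled and would raise the requirement further. The power figures apply to a BW-type test like that in SAP 6.2, without baseline adjustment, not to the likelihood ratio test selected in Appendix C.

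A reader might also infer that the Objective 2 power claim itself fails. It does not: over 80% power for RR_ITT below 0.65 at tau 0.23 is reproduced and does not depend on f. Only the translation into a proportion treated is affected.

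**What to change.** In SAP 6.2.1, state the assumed treatment start time and exposure fraction, and say whether RR_treated is an on-treatment rate or a full-window average. Recompute the p_treat table as (1 - RR_ITT)/[f(1 - RR_treated)] over a range of f, keeping f = 1 as a row labelled as no start-up delay. In 6.2.2, replace the 39-44% conclusion with the resulting range and its assumptions. The cost is one recalculated table, some wording and a less favourable stated figure. Trial conduct and the primary Objective 2 analysis do not change.

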## 7.0 DESCRIPTIVE ANALYSES

### 7.1 Analyses of Demographic and Baseline Data

The demographic variables for this study include age, sex, race/ethnicity, zip code-based characteristics (e.g., census variables), and type of insurance. The baseline clinical characteristics include diagnoses of medical conditions, mental health disorders, substance use disorders, and co-morbidity indices.

Descriptive statistics for baseline and demographic variables will be presented for the randomized clinics and for participants assigned to the clinics, overall and separately for each of the treatment arms (as well as secondary analyses within each HCS). Descriptive statistics will include N, mean, standard deviation, median, 25th and 75th percentiles, minimum and maximum for continuous variables and proportions and percentages for categorical variables. Since randomization is expected to produce balance at baseline between the two arms of the trial, statistical comparisons of treatment groups with respect to baseline characteristics will not be conducted. The updated CONSORT statement for parallel group-randomized trials no longer recommends formal testing of statistical significance of differences between baseline characteristics.

### 7.2 Crossover

For all measures described below, patients will be assigned to a primary care clinic based on the algorithm stipulated above in the SAP (Section 3.0).

#### 7.2.1 Main measures of Crossover of Patients with OUDs and Treated for OUDs

We will describe cross-over in terms of the following key measure:

Cross-over between clinic arms*	The number of patients with OUDs assigned to each clinic (PROUD and UPC) in the pre-randomization period who are seen in the other clinic post-randomization.
--	---

For this measure, we will evaluate crossover in both directions, each separately (from PROUD to UPC and vice versa). However, the main analysis of interest will be the proportion of UPC patients with OUD diagnosed prior to randomization who are treated for OUDs in a PROUD clinic post-randomization.

#### 7.2.2 Other General Measures of Crossover

In addition to evaluating crossover among patients with an OUD diagnosis in the 3 years prior to randomization, we will also describe crossover more generally, among all patients seen in the primary care clinic. Specifically, crossover will be defined as occurring if a patient assigned to a clinic in one arm of the trial (PROUD or UPC) during the 3 years prior to randomization is seen in a clinic in the other arm post-randomization. As above, we will evaluate crossover in both directions (separately), with the main analysis of interest the proportion of UPC patients who are treated for OUDs in a PROUD clinic post-randomization.

#### 7.2.3 Crossover of Providers

If we observe that patients assigned to the UPC clinic (with or without an OUD diagnosis) are treated for OUDs post-randomization in the PROUD intervention clinic or vice versa, we will examine crossover of PC providers who prescribe buprenorphine. Specifically, we will examine whether PC providers move between randomized PROUD intervention and UPC clinics.

### 7.3 Implementation

We will describe, in each of the PROUD intervention clinics, the time from randomization until the NCM was (1) hired, (2) trained in Boston, (3) engaged the first patient in care in the PROUD intervention clinic, (4) left the study; (5) second NCM hired; and (6) engaged the first 10 patients in care in the PROUD intervention clinic. We will also summarize other relevant implementation milestones, such as when the Boston Training and Technical Assistance team conducted a clinic visit as well as those captured by the weekly NCM reports:

#### For each week

- # of New starts
- # of Re-engagements
- # of Transfers (patients new to NCM who were already on treatment)
- # of Discharges

#### Cumulative

- Total Ever Treated on Meds
- Total Currently Treated on Meds
- # of Starts for injectable BUP, Oral BUP, Oral NTX, Injectable NTX
- # of Re-engagements
- # of Transfers (patients new to NCM who were already on treatment)

### 7.4 Characteristics of Treated Patients

Key components of the PROUD intervention are to increase documentation and treatment of OUD among patients already in the clinic, and to attract new patients to receive care in the clinic who have not been seen previously in the clinic or who may be new to the HCS entirely. We therefore plan to describe, overall and by intervention arm, the proportion of patients with medication treatment for OUDs after randomization who were

- 1) In the clinic pre-randomization and
  - a. had an EHR-documented OUD diagnosis (“documented OUD”) pre-randomization
  - b. did not have documented OUD pre-randomization
- 2) Not in the clinic pre-randomization and
  - a. were seen pre-randomization in the clinic of the HCS that was randomized to the other arm of the trial
    - i. With documented OUD pre-randomization
    - ii. Without documented OUD pre-randomization
  - b. were seen pre-randomization in a different clinic of the HCS that was not randomized
    - i. With documented OUD pre-randomization
    - ii. Without documented OUD pre-randomization
  - c. were not seen pre-randomization in the HCS

We will also describe these proportions among patients who engaged with the NCM.

